1. BACKGROUND AND RATIONALE

1.1 Medical Background and Short Rationale for the Clinical Study

Botulinum toxin (BoNT) is a potent neurotoxic protein produced by the Gram-positive anaerobic bacterium, *Clostridium botulinum*. The molecule is produced naturally by these bacteria together with a series of accessory proteins, forming what is termed the “toxin complex”. The neurotoxin is the cause of the severe and potentially fatal disease of botulism. In addition, the protein is used in very small quantities as a treatment modality for aesthetic and medical indications, many of which are characterized by increased muscle activity. Botulinum toxins occur in seven known serotypes (A-G) that are produced by different strains of *Clostridium botulinum*. Clinically-important biologic activity is limited primarily to the A and B serotypes, of which the type A serotype (BoNT-A) is used widely throughout the world for the treatment of a range of clinical conditions.

BoNT-A blocks the release of acetylcholine into the neuromuscular junction (synapse) cleft, thereby prohibiting the activation of acetylcholine receptors. Paresis by chemical denervation thus occurs in the target muscle, leading to inhibition of muscular contraction. The active neurotoxin is 150 kDa molecular weight and QM1114-DP only contains this part of the toxin complex: there are none of the other accessory proteins which are normally associated with the 150 kDa active moiety.

Since the 1970s, BoNT-A has been investigated and subsequently approved for the treatment of multiple indications around the world.^{2,3} Treatment of strabismus by relaxation of overactive extraocular muscles was the first reported medical use.⁴ Clinical studies for aesthetic indications were first performed in the late 1980s.⁵ Since then, many other clinical indications have been investigated,⁶⁻⁸ although the number of approved indications is much smaller. BoNT-A products have been licensed in the US for the aesthetic indications of glabellar lines (GL), lateral canthal lines (LCL) and forehead lines (FL), together with therapeutic indications such as strabismus, blepharospasm, hemifacial spasm, cervical dystonia, focal spasticity, prophylactic treatment of chronic migraine, overactive bladder and hyperhidrosis.

In the early 1990s, patients treated with BoNT-A for blepharospasm were observed to lose their frown lines and,^{5,9} since publishing these observations, the use of BoNT-A in the aesthetic setting has accelerated. Injectable BoNT-A products have been investigated for multiple aesthetic indications in attempts to reverse the appearance of aging, especially in the facial region.² In the treatment of facial lines, the effect of BoNT-A injections usually persists for approximately 4-6 months. Facial muscle activity and severity of the facial wrinkles then returns to baseline. Full functionality of facial muscles is usually restored by approximately 6 months post-treatment.¹⁰

There are four BoNT-A products currently licensed in the United States (US) for the treatment of GL (Botox Cosmetic®, Dysport®, Xeomin® and Jeuveau™), and one licensed for the treatment of LCL (Botox Cosmetic®). QM1114-DP is a novel botulinum toxin type-A1 which is presented as a liquid formulation. Unlike the main commercially available botulinum toxins in the US, QM1114-DP is manufactured and formulated without any animal or human proteins. As a novel BoNT-A with a differentiated formulation, QM1114-DP is being developed for the treatment of moderate to severe GL and LCL in adults over 18 years.

 GALDERMA	<small>Title</small> 43QMI902 Clinical Study Protocol - QM1114 - LCL and GL	<small>Doc id</small> MA-40371
--	---	--

1.2 Study Product Profile

1.2.1 Drug Profile

QM1114 is a protein dimer of 150 kilodalton (kDa) **CCI**

Unlike other commercially

available BoNTs, QM1114 is manufactured and formulated without any animal or human proteins, thereby reducing the potential risk of viral contamination in the product.

CCI

1.2.2 Pre-Clinical Documentation

The pre-clinical pharmacology-toxicology program has included appropriate toxicology studies to support safety for administration of QM1114-DP at the proposed dose of 50 unit (U), 60 U, and combined total dose of 110 U which will be evaluated in this study.

CCI

No safety pharmacology or pharmacokinetic studies were conducted for QM1114-DP since no systemic exposure to the product is expected with a single IM administration to specific facial muscles using the dose proposed. Additionally, BoNT-A binds with high affinity at the neuronal synapses at the local injection site.¹¹ Therefore, any metabolism and elimination of the product would occur at the local site of injection.

CCI

 GALDERMA	<small>Title</small> 43QMI902 Clinical Study Protocol - QM1114 - LCL and GL	<small>Doc id</small> MA-40371
---	--	-----------------------------------

[figure not shown]
Effective date: 2020-06-09 07:02

Effective

Version: 4.0

CCI

1.2.3 Clinical Documentation

 GALDERMA	<small>Title</small> 43QMI902 Clinical Study Protocol - QM1114 - LCL and GL	<small>Doc id</small> MA-40371
---	--	-----------------------------------

Effective date: 2020-06-09 07:02

Effective

Version: 4.0

CCI

Effective date: 2020-06-09 07:02

 GALDERMA	<small>Title</small> 43QMI902 Clinical Study Protocol - QM1114 - LCL and GL	<small>Doc id</small> MA-40371
---	--	-----------------------------------

Effective

CCI

CTN 43QMI1313

Following successful completion of clinical study CCI [REDACTED], a randomized, double-blind, placebo controlled, dose finding study of QM1114-DP using three different single doses of QM1114-DP (30, 45, 60 U) in male or female subjects aged over 18 years with moderate to very severe GL was performed.

Efficacy in reduction of GL severity was evaluated using the 5-point MAS scale. Efficacy assessments were made for up to and including six months post-treatment.

CCI

Version: 4.0

 GALDERMA	Title 43QMI902 Clinical Study Protocol - QM1114 - LCL and GL	Doc id MA-40371
--	---	----------------------------------

CCI

1.2.4 Dose Rationale

Non-clinical studies have shown a similarity between QM1114-DP potency units and Speywood units (i.e., the Dysport®/Azzalure® product). In the treatment of the LCL with Speywood units the recommended dose is 60 U. In the treatment of the GL with Speywood units the recommended dose is 50 U.

For treatment of the LCL and GL, alone or in combination, both the safety and efficacy of QM1114-DP was established in the phase 1 study (CCI [REDACTED]). For treatment in the LCL the 60 U dose has been selected for further clinical development, and for treatment in the GL the 50 U dose has been selected. For the combined LCL and GL treatment, QM1114-DP was evaluated at two ascending dose levels (i.e., 110 U [50 U in the GL and 60 U in the LCL], and 140 U [50 U in the GL and 90 U in the LCL]). The 110 U dose has been selected for further clinical development in the treatment of LCL and GL. This is consistent with the combined recommended Speywood unit doses in each treatment area as well as clinical experience, as specified above.

1.3 Risk/Benefit Assessment

CCI

In the phase 2 study (CTN 43QM1313; GL treatment area only), QM1114-DP was well tolerated at all dose levels. The treatment-related TEAEs reported in the study were of similar type as those reported for other toxins in GL treatment. CCI [REDACTED]

The risk of AEs occurring may be reduced by using physicians who are experienced in the botulinum toxin injection technique. All treating Investigators will be trained in the administration technique of QM1114-DP prior to the study start.

The benefit to subjects receiving QM1114-DP in this study will be a temporary reduction in the appearance of their LCL and/or GL. The subjects in the placebo group are not expected to gain any clinical benefit from their participation in the study; however, as this is an aesthetic indication there are no sequelae to lack of efficacy beyond a disappointment in the reduction of severity of their LCL and/or GL. In addition, only one subject out of seven will receive placebo only in the study; most subjects (6/7 subjects) will receive QM1114-DP in one or both treatment areas (i.e., LCL and/or GL).

 GALDERMA	Title 43QMI902 Clinical Study Protocol - QM1114 - LCL and GL	Doc id MA-40371
--	---	----------------------------------

No additional risks specific to the QM1114-DP 50 U, 60 U, and 110 U doses are anticipated, and sufficient clinical experience with BoNT-A products with similar mode of action for facial aesthetic use at dose levels corresponding to the dose levels in this study demonstrate the potential benefit of the proposed treatments. Adverse events will be recorded at each study visit, and subjects will also be queried for any potential signs and symptoms of local and distant spread of the toxin effect.

In conclusion, given the anticipated low level of transient and acceptable risks, the risk/benefit assessment of the use of QM1114-DP for the treatment of moderate to severe LCL and GL, and appears to offer a substantial clinical benefit at reasonable risk.

2. CLINICAL STUDY OBJECTIVES, ENDPOINTS, AND CLINICAL HYPOTHESIS

2.1 Clinical Study Objectives

The objective of the study is to evaluate the efficacy and safety of a single dose of QM1114-DP for the treatment of moderate to severe LCL and GL, alone or in combination.

2.1.1 Primary Efficacy Objectives and Endpoints

The primary objective of this study is to evaluate the efficacy of a single dose of 60 U of QM1114-DP in the LCL and 50 U of QM1114-DP in the GL, alone or in combination, compared to placebo for the treatment of moderate to severe LCL and GL.

GL

For the primary endpoint, the composite responder rate will be evaluated at Month 1 using the GL-ILA and the GL-SLA at maximum frown. A composite responder is defined as a subject who achieves grade/level 0 or 1 in GL severity and at least 2 grades improvement from baseline on both the GL-ILA and GL-SLA scales concurrently.

LCL

For the primary endpoint, the composite responder rate will be evaluated at Month 1 using the LCL-ILA and the LCL-SLA at maximum smile. A composite responder is defined as a subject who achieves grade/level 0 or 1 in LCL severity and at least 2 grades improvement from baseline on both the LCL-ILA and LCL-SLA scales concurrently.

2.1.2 Secondary Efficacy Objectives and Endpoints

The secondary efficacy objectives and endpoints of the study are:

Objective: To evaluate the efficacy of a single dose of 60 U of QM1114-DP in the LCL and 50 U of QM1114-DP in the GL, alone or in combination, and placebo for the treatment of moderate to severe LCL and GL.

Endpoint: Percentage of subjects who achieve a score of 0 or 1 at:

 GALDERMA	<small>Title</small> 43QMI902 Clinical Study Protocol - QM1114 - LCL and GL	<small>Doc id</small> MA-40371
---	--	-----------------------------------

Effective date: 2020-06-09 07:02

Effective

Version: 4.0

CCI

- Each post-treatment visit (excluding month 1) using the GL-ILA at maximum frown
- Each post-treatment visit (excluding month 1) using the LCL-ILA at maximum smile

CCI

 GALDERMA	<small>Title</small> 43QMI902 Clinical Study Protocol - QM1114 - LCL and GL	<small>Doc id</small> MA-40371
---	--	-----------------------------------

Effective date: 2020-06-09 07:02

Effective

Version: 4.0

CCI

 GALDERMA	Title 43QMI902 Clinical Study Protocol - QM1114 - LCL and GL	Doc id MA-40371
--	---	----------------------------------

2.1.4 Safety Objectives and Endpoints

To evaluate the safety of a single dose of 60 U of QM1114-DP in the LCL and 50 U of QM1114-DP in the GL, alone or in combination, compared to placebo for the treatment of moderate to severe LCL and GL.

Safety endpoints include:

- Incidence and severity of TEAEs
- Focused physical examination (FPE) findings
- Vital signs
- Electrocardiogram (ECG)
- Laboratory parameters (clinical chemistry and hematology)
- Neutralizing antibody production

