All efficacy, safety and baseline characteristics variables will be presented using descriptive statistics within each treatment group, and graphs as appropriate. Continuous data will be summarized using n (number of observations), mean, standard deviation, median, minimum and maximum value, while categorical data will be presented by n and percentages. All data will also be listed in subject data listings.

Subject disposition, completion and discontinuation by study visit, protocol deviations, demographics and baseline characteristics, medical history, medical and surgical procedures, prior and concomitant medications, will be summarized by treatment group.

For analysis of duration of response and time to onset of treatment response, Kaplan-Meier plots and estimates of the median event times will be used.

 GALDERMA	Title 43QMI902 Clinical Study Protocol - QM1114 - LCL and GL	Doc id MA-40371
--	---	----------------------------------

9.1.3.1 *Subgroup Analysis*

Analysis on the proportion of composite responders at Month 1 as measured by the ILA and the SLA at maximum smile and maximum frown, separately, will be performed in the following subgroups:

- Gender
- Baseline severity score of the ILA of LCL severity at maximum smile
- Baseline severity score of the ILA of GL at maximum frown
- Previous treatment with BoNT-A
- Fitzpatrick skin type

For duration of response, a subgroup analysis using only subjects with at least 2 point improvement on the LCL-ILA and GL-ILA, respectively will be conducted. Thus, duration of response will be analyzed based on the full ITT population as well as a subgroup analysis.

9.1.3.2 *Safety Analysis*

All treatment related TEAEs by maximum intensity, treatment unrelated TEAEs by maximum intensity, treatment emergent SAEs by causality and maximum intensity, and action taken of treatment related TEAEs will be summarized by SOC and PT including number of subjects with at least one event, percentages, and number of events. All related TEAEs will also be summarized by time to onset and duration. In addition, a short summary of these presentations will be provided.

Data for hematology, blood chemistry, antibodies, and vital signs will be summarized by descriptive statistics with the value at each visit as well as the change from baseline. Results of ECGs will be summarized descriptively. The results of the urine pregnancy tests will be listed

9.1.4 **Withdrawals and Deviations**

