1.5.1 Adverse events

Adverse events (AEs) are to be monitored throughout the course of the study. All AEs reported will be coded using the Medical Dictionary for Regulatory Activities (MedDRA, version in force at the time of database freeze) and classified by MedDRA preferred term (PT) and system organ class (SOC). AEs will be defined as treatment-emergent adverse events (TEAEs) if the AE had an onset time greater than or equal to the time of study treatment. The study period for the purpose of AE collection is defined as the period from the signing of a study specific informed consent to study exit.

A two-point scale ("Yes" or "No" response) will be used for the causality assessments. The

 GALDERMA	Title 43QMI902 Statistical Analysis Plan US - QM1114-DP - GL&LCL	Doc id MA-43265
--	---	----------------------------------

Effective date: 2021-02-05 13:16

Effective

Version: 1.0

Treating Investigator should be asked to indicate a response to each of the following questions in the electronic Case Report Form (eCRF):

- “Do you consider that there is a reasonable possibility that the event may have been caused by the study product?”
- “Do you consider that there is a reasonable possibility that the event may have been caused by the study product injection procedure?”

If either of these questions is answered with a ‘Yes’, the AE will be considered related.

AE endpoints include incidence and severity of TEAEs.

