2.5.2 Adverse events

All AE data will be summarized by treatment group. Missing dates will be imputed as described below. AEs will be summarized by SOC and PT. AEs occurring before treatment will be presented in listings only. The MedDRA version used for the coding will be noted as a footnote in the tables and listings.

A summary of all AEs will be provided, which will include:

- number (%) of subjects who did not have an AE
- number (%) of subjects with at least one TEAE and number of events
- number (%) of subjects with at least one TEAE related to study product or injection procedure
- number (%) of subjects with at least one TEAE not related to study product or injection procedure
- number (%) of subjects with at least one TEAE leading to discontinuation
- number (%) of subjects with at least one serious TEAE.

Summaries of TEAEs (including the total number of events, number and percentage of subjects) will be displayed by treatment group according to the following:

- All TEAEs by SOC and PT
- Treatment emergent SAE by SOC, PT, maximum intensity (mild, moderate, severe) and causality
- Related TEAEs by SOC and PT, and maximum intensity (mild, moderate, severe)
- Unrelated TEAEs by SOC and PT, and maximum intensity (mild, moderate, severe)
- TEAEs leading to discontinuation by SOC and PT, and maximum intensity (mild, moderate, severe)
- TEAEs by SOC, PT, and action taken (none, medical treatment, non-pharmacological treatment, subject withdrawn)

For the subject level analyses, the number and percentage of subjects who experienced at least one of the events listed above will be summarized overall and for each SOC and each PT. System organ class and PTs will be presented in descending frequency first (by the QM1114-DP in GL/QM1114-

 GALDERMA	Title 43QMI902 Statistical Analysis Plan US - QMI114-DP - GL&LCL	Doc id MA-43265
--	---	----------------------------------

Effective date: 2021-02-05 13:16

Effective

Version: 1.0

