14.3 Safety Data			
14.3.1 - 14.3.6 Exposure and Adverse Events			
14.3.1	Injection Administration and Characteristics	Safety	U
14.3.2	Overall Summary of Adverse Events	Safety	U

Table Number	Table Title	Analysis Population	(U)nique/ (R)epeat
14.3.3.1	Treatment Emergent Adverse Events by MedDRA System Organ Class and Preferred Term	Safety	U
14.3.3.2	Serious Treatment Emergent Adverse Events by Intensity, MedDRA System Organ Class and Preferred Term	Safety	U
14.3.3.3	Treatment Emergent Adverse Events Related to Study Product or Injection Procedure by Intensity, MedDRA System Organ Class and Preferred Term	Safety	R
14.3.3.4	Treatment Emergent Adverse Events That Led to Discontinuation by Intensity, MedDRA System Organ Class and Preferred Term	Safety	R
14.3.3.5	Treatment Emergent Adverse Events Unrelated to Study Product or Injection Procedure by Intensity, MedDRA System Organ Class and Preferred Term	Safety	R
14.3.3.6	Treatment Emergent Adverse Events Related to Study Product or Injection Procedure by Intensity, MedDRA System Organ Class and Preferred Term by Age	Safety	U
14.3.3.7	Treatment Emergent Adverse Events Related to Study Product or Injection Procedure by Intensity, MedDRA System Organ Class and Preferred Term by Study Site	Safety	U
14.3.3.8	Treatment Emergent Adverse Events Related to Study Product or Injection Procedure by Intensity, MedDRA System Organ Class and Preferred Term by Fitzpatrick Skin Type	Safety	U
14.3.3.9	Treatment Emergent Adverse Events Related to Study Product or Injection Procedure by Intensity, MedDRA System Organ Class and Preferred Term by Race	Safety	U
14.3.3.10	Treatment Emergent Adverse Events Related to Study Product or Injection Procedure by Intensity, MedDRA System Organ Class and Preferred Term by Gender	Safety	R
14.3.3.11	Treatment Emergent Adverse Events Related to Study Product or Injection Procedure by Intensity, MedDRA System Organ Class and Preferred Term by Prior Botulinum Toxin Use	Safety	R
14.3.4	Summary of Duration of Adverse Events Related to Study Product or Injection Procedure by System Organ Class and Preferred Term	Safety	U
14.3.5	Summary of Number of Days to Onset of Adverse Events Related to Study Product or Injection Procedure by System Organ Class and Preferred Term	Safety	R
14.3.6	Summary of Action Taken for Treatment Emergent Adverse Events Related to Study	Safety	U

2021-02-05 13:16

Effective date:

Effective

Version: 1.0

Table Number	Table Title	Analysis Population	(U)nique/ (R)epeat

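### Severity of TEAEs is a named safety endpoint, but no planned table shows intensity for all TEAEs by arm; it appears only within subsets

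*Protocol*

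**What the plan says.** **Endpoint.** Protocol 2.1.4 lists "Incidence and severity of TEAEs" among the safety endpoints, under an objective of comparison with placebo. SAP 1.5.1 restates it: "AE endpoints include incidence and severity of TEAEs". Neither document restricts it by causality, seriousness or any other feature.

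**Planned analysis in the protocol.** Section 9.1.3.2 plans intensity for three groups: "All treatment related TEAEs by maximum intensity, treatment unrelated TEAEs by maximum intensity, treatment emergent SAEs by causality and maximum intensity".

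**Planned analysis in the SAP.** Section 2.5.2 plans a summary of every TEAE, "All TEAEs by SOC and PT", with no intensity. Intensity is planned for serious events ("Treatment emergent SAE by SOC, PT, maximum intensity (mild, moderate, severe) and causality"), for related events, for unrelated events and for events leading to discontinuation. The overall AE summary has six items: no AE, any TEAE, related, not related, leading to discontinuation, and serious. None concerns intensity.

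**Table list (SAP 4.1).** Table 14.3.3.1 is titled "Treatment Emergent Adverse Events by MedDRA System Organ Class and Preferred Term". The titles of 14.3.3.2 to 14.3.3.11 and of 14.3.7.1 to 14.3.7.3 include intensity, each for a subset.

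**The concern.** A reader of the study report will want to know, for each arm, how many subjects had at worst a mild, a moderate or a severe adverse event. That is a natural summary of the severity half of the endpoint. The plan gives the incidence half for all TEAEs and leaves the severity half in pieces.

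The pieces that together cover all TEAEs are the related and unrelated tables. Under SAP 2.5.2 a subject counts at most once per category, so a subject with one related and one unrelated event is counted once in each table. The subject-level severity profile of an arm therefore cannot be read from the planned output, nor can its contrast with placebo. At stake is whether a named safety endpoint can be reported by arm at subject level. No efficacy conclusion is at stake.

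**Working it through.** There is no planned figure to reproduce. The check is an inventory of tables, followed by bounds on what can be recovered.

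**Step 1: inventory of AE tables (SAP 4.1, read with SAP 2.5.2).**

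| Table | Events covered | Intensity shown |
|---|---|---|
| 14.3.2 | All TEAEs (overall summary) | No |
| 14.3.3.1 | All TEAEs | No |
| 14.3.3.2 | Serious | Yes |
| 14.3.3.3 | Related | Yes |
| 14.3.3.4 | Leading to discontinuation | Yes |
| 14.3.3.5 | Unrelated | Yes |
| 14.3.3.6 to 14.3.3.11 | Related, by subgroup | Yes |
| 14.3.7.1 to 14.3.7.3 | Suspected local spread, remote spread, hypersensitivity | Yes |

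Tables with intensity for all TEAEs: 0. Tables with intensity within a subset: 10 (14.3.3.2 to 14.3.3.11) + 3 (14.3.7.1 to 14.3.7.3) = 13.

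**Step 2: what can be added.** An event is related if either causality question is answered yes, and otherwise unrelated, so the two tables divide all TEAEs. For events, severe total = severe related + severe unrelated. This is exact if the event counts are shown per intensity level.

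For subjects, let a be the number in an arm of n with a severe related TEAE, b the number with a severe unrelated TEAE, and k the number with both. Then

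any severe = a + b − k.

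No planned table gives k. It is at least 0 and at most the smaller of a and b, so the two tables give

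max(a, b) ≤ any severe ≤ min(n, a + b).

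While a + b does not exceed n, the width of this range is min(a, b). It vanishes when either count is zero.

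**Step 3: a partial tightening.** Table 14.3.2 will give subjects with any TEAE (T), any related TEAE (R) and any unrelated TEAE (U). Subjects with both kinds at any intensity number c = R + U − T. Since k cannot exceed c, the lower limit rises to a + b − c whenever c is below min(a, b). The answer is exact if c is zero. Otherwise a range remains.

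**Step 4: size, with assumed counts.** The arm sizes of 118 and 59 are the planned ones (Protocol 3). The event counts below are assumptions and appear in neither document. The ranges use the Step 2 limits.

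| Arm | a | b | Any severe | Percent |
|---|---|---|---|---|
| Active, n = 118 | 5 | 4 | 5 to 9 | 5/118 = 4.2% to 9/118 = 7.6% |
| Active, n = 118 | 8 | 5 | 8 to 13 | 8/118 = 6.8% to 13/118 = 11.0% |
| Placebo, n = 59 | 1 | 3 | 3 to 4 | 3/59 = 5.1% to 4/59 = 6.8% |

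For the last two rows the difference from placebo could be as small as 8/118 − 4/59 = 0.0 points or as large as 13/118 − 3/59 = 5.9 points. These limits need complete overlap in one arm and none in the other. With smaller counts the range shrinks: if min(a, b) is 1, the uncertainty is one subject, 1/118 = 0.8% of an active arm or 1/59 = 1.7% of placebo.

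**The case against.** The best case for the plan is that the severity of every TEAE is already tabulated by arm, in two tables instead of one. Causality is a forced yes or no, SAP 2.5.2 calls for event totals as well as subjects, and Listing 16.2.7.1 shows all AEs. Protocol 9.1.3.2 and SAP 2.5.2 agree on the related and unrelated split. Both documents also say in general terms that safety variables will be summarised descriptively by treatment group. Safety is descriptive throughout, and few severe events may occur.

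Most of this stands. Event counts can be recovered if shown per intensity level, the data are complete, and the gap in numbers may be small. It does not supply the subject-level distribution, though. The general sentence names no table, the specific lists omit one, and a listing is not a summary by arm.

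Three stronger readings are tempting, and the documents do not support them.

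- *That worst grade per subject is the endpoint as defined.* Neither section defines how severity is to be summarised. Worst grade per subject is a natural summary, and maximum intensity is the measure the SAP uses elsewhere.
- *That all planned severity output passes through the investigator's causality opinion, and so would mislead.* The serious and discontinuation tables are not selected on causality. The related and unrelated tables will both be available, so a shift of events from one to the other would show. That attribution will differ by arm because the effect is visible is conjecture.
- *That an all-TEAE table would make severity free of investigator judgement.* Under Protocol 7.2.6.1.6 the investigator also grades intensity by medical judgement. The added table removes the causality split and nothing more.

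**Conclusion.** The point holds as a gap in descriptive reporting. Severity of TEAEs is an unrestricted endpoint in both documents, and none of the 13 tables with intensity covers all TEAEs. The number of subjects by maximum TEAE intensity in each arm cannot in general be recovered from the planned tables. For severe events, the related and unrelated tables leave an uncertainty of up to min(a, b) subjects per arm, which Table 14.3.2 may narrow.

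This rests on the table titles and the content listed in SAP 2.5.2, since the table layouts are not part of the documents. The percentages shown rest on assumed counts. No data are lost, and the primary efficacy analysis, the type I error control and the sample size are unaffected.

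**What to change.** 1. In SAP 2.5.2, replace "All TEAEs by SOC and PT" with *All TEAEs by SOC, PT and maximum intensity*, and extend Table 14.3.3.1 and its title to match.
2. Add to the overall summary in SAP 2.5.2 (Table 14.3.2) the number and percentage of subjects by maximum intensity of any TEAE (mild, moderate, severe), for each of the four arms. Naming the four arms is useful because SAP 2.1 describes the treatment groups only as active and placebo.
3. State that these rows summarise the severity part of the Protocol 2.1.4 endpoint, and that the related and unrelated tables support them.

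The cost is a change of SAP wording and one added classification in two existing tables. Intensity is already recorded for every AE, so no new data are needed. A change after the SAP is final is permitted if the study report describes it (Protocol 9.1, SAP 2.1).
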